1. OBJECTIVES

1.1 Study Design

Within the gastroenterology practice of Massachusetts General Hospital (MGH), we will conduct a prospective, single-arm clinical trial to measure the effects of daily 4-gram eicosapentaenoic acid (EPA), through treatment with AMR101 (VASCEPA, icosapent ethyl) on urine, stool and tissue biomarkers associated with colorectal cancer.

1.2 Primary Objectives

To measure the effect of daily 4-gram AMR101 treatment on fatty acid composition in colorectal tissue among individuals with a history of colorectal adenoma.

1.3 Secondary Objectives

To measure the effect of EPA treatment on the gut microbiome and metabolome, urinary prostaglandin metabolites (PGE-M) and gene expression profile of colorectal tissue among individuals with a history of colorectal adenoma.

2. BACKGROUND

2.1 Study Disease(s)

Colorectal cancer is the third most common cancer and third leading cause of cancer-related deaths in the U.S. In 2016, an estimated 95,270 new cases of colorectal cancer will be diagnosed and 49,190 people will die from the disease.¹ Age is strongly associated with colorectal cancer incidence, with more than a third of all colorectal cancer deaths occurring in the population aged 80 years or older. The death rates are higher in black populations and lowest in Asian individuals. Men have a slightly higher lifetime probability of receiving a colorectal cancer diagnosis (5.0%) compared to women (4.7%).²

Nationally, incidence rates have been declining over the past two decades; and at a slightly higher rate over the last 10 years compared to the 1990s. This is largely believed to be due to increasing use of screening methods and improved risk factor profile. Still the public health concern remains as colorectal cancer ranks third among all cancer deaths with only an approximate 65% five-year survival rate, necessitating further advances in cancer prevention.²

2.2 IND Agent(s)

N/A; Exempt.

This study will investigate the effects of standard-dose EPA treatment using the FDA-approved drug AMR101, and meets the five exemption criteria as laid out by 21 CFR 312.2(b):

- The drug product is lawfully marketed in the United States.
 - The drug AMR101 used for the study is FDA approved and lawfully marketed in the United States.
- The investigation is not intended to be reported to FDA as a well-controlled study in support of a new indication and there is no intent to use it to support any other significant change in the labeling of the drug.
 - The end points of the study are mechanistic biomarkers related to EPA and are not used in any clinical context.
- In the case of a prescription drug, the investigation is not intended to support a significant change in the advertising for the drug.
 - The study aims to investigate the potential anti-cancer mechanisms of EPA and is not intended to support any change in the advertising for the drug AMR101.
- The investigation does not involve a route of administration, dose, patient population, or other factor that significantly increases the risk (or decreases the acceptability of the risk) associated with the use of the drug product (21 CFR 312.2(b)(1)(iii)).
 - AMR101 used in the proposed study is made of ethyl esters of the omega-3 fatty acid, eicosapentaenoic acid (EPA), which are natural substances found in the oil of certain fish, and will be orally administered in a standard dose (4 g/day) in people who are being evaluated for colorectal cancer.
- The investigation is conducted in compliance with the requirements for review by an IRB (21 CFR part 56) and with the requirements for informed consent (21 CFR part 50).
 - The protocol will be submitted to the Dana Farber/Harvard Cancer Center IRB, who will also review the informed consent documents.
- The investigation is conducted in compliance with the requirements of § 312.7 (i.e., the investigation is not intended to promote or commercialize the drug product).
 - The study is not intended to promote or commercialize any drug product.

Our application for an IND exempt has been approved by the Division of Oncology Products 2 (DOP2) of the FDA (see the attached formal letter, IND 141418. Please note that the name of the study has been changed since receipt of the IND approval).

2.3 Other Agent(s)

AMR101

AMR101 (icosapent ethyl) is a prescription medicine for adults to lower blood levels of triglycerides. It is supplied as a liquid-filled gel capsule for oral administration. The standard dose is 4 g per day (administered as 8 half-gram capsules). Each 0.5-gram capsule of AMR101 contains 0.5 gram of icosapent ethyl, which is an ethyl ester of the omega-3 fatty acid eicosapentaenoic acid (EPA).

EPA possesses triglyceride-lowering and anti-inflammatory activities, and has been suggested to be beneficial for a variety of health outcomes in adults, including coronary heart disease,³ stroke,⁴ type 2 diabetes,⁵ depression,⁶ and inflammatory bowel disease,⁷ although the data are not univocal.⁸ Increasing evidence supports the anticancer effect of EPA.⁹

Besides EPA, AMR101 capsules also contain the following inactive ingredients: tocopherol, gelatin, glycerin, maltitol, sorbitol, and purified water.

2.4 Rationale

Colorectal cancer is the third leading cause of cancer-related deaths in the US.¹ Substantial data support the benefit of EPA for colorectal cancer prevention and treatment,¹⁰ which may be mainly due to the immunomodulatory and anti-inflammatory activity of EPA.¹¹ Increasing data support that gut microbes are pivotal in integrating dietary cues with host immunity, and that disturbances in the gut microbiota may promote colorectal cancer by breakdown of intestinal immune homeostasis. Dietary fat composition is a major driver of the gut microbial community structure and EPA has been shown to enrich the gut bacteria that possess immunoprotective activities. These data together our hypothesis that EPA modulates the gut microbiota to preserve colorectal immune homeostasis and suppress colorectal cancer. In the current study, we propose to experimentally test this hypothesis by assessing the effect of EPA supplement on the gut microbiota - host immune interaction.

2.5 Correlative Studies Background

2.5.1 EPA and colorectal cancer

Several lines of evidence support the benefit of EPA for colorectal cancer prevention and treatment.¹⁰ In a meta-analysis of 3 prospective cohort studies and 8 case-control studies, high levels of EPA are associated with lower risk of colorectal cancer in a dose-dependent manner.¹² In an RCT of patients with familial adenomatous polyposis, EPA supplement of 2 g daily for 6 months reduces the number and size of polyps by 20-30%, an effect comparable to that by the FDA-approved prostaglandin-endoperoxide synthase 2 (PTGS2, also known as COX-2) inhibitors.¹³

2.5.2 Immune mechanisms underlying the anticancer effect of EPA

The anticancer effect of EPA may be related to its multifaceted immunomodulatory activity mediated by alterations in lipid raft structure and changes in fatty acid composition of cell membranes.¹⁴ These changes alter gene expression and the activities of several key immune signaling pathways, such as PTGS2 and nuclear factor kappa-light-chain-enhancer of activated B cells (NF- κ B), and modify downstream metabolite production, including a decrease in proinflammatory eicosanoids (e.g., prostaglandin E₂; PGE₂) and an increase in pro-resolving lipid mediators (e.g., resolvin and protectin).¹⁴⁻¹⁹ Of note, PGE₂ has been suggested as one of the critical pathways that govern tumor-mediated immune dysfunction and contributes to a shift in the tumor microenvironment from anti-tumor responses to immunosuppressive responses.²⁰ On the other hand, increasing data suggest that EPA may revert the immune suppression mediated by Treg cells.^{21,22} Treatment of Tregs with EPA decreases the immune suppressive activity by downregulating inhibitory precursors.²¹ In experimental colorectal cancer models, fish oil exerts its antitumor effect by altering Tregs and their cytokine repertoire (e.g., reduction of IL-10 expression).²² In an RCT of 60 patients with solid tumors, supplementation of EPA increased the

ratio of T-helper cells to T-suppressor cells in the peripheral blood of the malnourished patients, and prolonged the survival of all the patients.²³

Our recent observational study indicated that high EPA intake was associated with lower risk of colorectal cancer that is infiltrated with a high density of FOXP3⁺ T cells, but not tumors with low densities of FOXP3⁺ T cells.²⁴ Similar benefit was observed when EPA and DHA were examined separately. Because FOXP3 is a prerequisite transcription factor for the immunosuppressive function of Treg cells, we further examined the *in vitro* effect of EPA on the suppressive activity of colorectal Treg cells against proliferation of T effector (Teff) cells.²⁴ Consistent with our human findings, we found that EPA treatment decreased the suppressive activity of FOXP3⁺ Treg cells in a dose-dependent manner. Of note, the suppressive effect of EPA leveled off at around 50 uM, which is within the normal range of EPA in human plasma samples, highlighting the human relevance of these experimental findings.

2.5.3 Gut microbiome in relation to EPA and colorectal cancer

Increasing data suggest that the gut microbiota play an important role in colorectal cancer development and progression, possibly by influencing both local and systemic immune response.²⁵ Among all potential shaping factors, diet is particularly important for the gut microbial composition and function. Compared to other types of fat, EPA has been associated with enhanced intestinal microbiota diversity and EPA-rich diet ameliorates omega-6 fatty acids- or antibiotics-induced dysbiosis.²⁶⁻²⁹ Animal studies indicate that EPA supplements increase the abundance of anti-inflammatory bacteria, such as lactic acid-producing bacteria (mainly *Lactobacillus* and *Bifidobacterium*), and decrease the abundance of immunosuppressive and pro-inflammatory bacteria, such as *F. nucleatum*, *Escherichia coli*, and *Akkermansia*. Administration of *Bifidobacterium* has been shown to improve patients' response to cancer immunotherapy,³⁰ whereas increased abundance of *F. nucleatum* has been linked to dampened antitumor immune response and poor prognosis of colorectal cancer.³¹⁻³³ Therefore, it is possible that the beneficial effect of EPA for colorectal cancer may be mediated by modulation of the gut microbial composition and function that in turn shape the host immune response.

3. PARTICIPANT SELECTION

Patients that meet the eligibility criteria will be identified through investigators during their routine clinical practice, supplemented by a periodic query of the MGH endoscopy (Provation) and pathology database. Patients also may be identified using Natural Language Processing clinical software that queries medical records. The MGH gastroenterologist that performed the procedure or saw the patient for outpatient care as follow-up to the patient's colonoscopy procedure will be notified and asked for permission to contact their patient. We plan to recruit patients who have undergone a colonoscopy by an MGH gastroenterologist either in the ambulatory clinic or for an endoscopic procedure. In some cases, these physicians may not be members of the study team. However, non-study physicians will not perform study-related procedures.

For appropriate patients, we will identify their preference for contact about research studies (Research Opportunities Direct to You [RODY] status) through queries of the Research Patient Data Registry (RPDR). Participants with a RODY YES response will be contacted by a letter (attached recruitment letter for RODY YES patients) from the study PI. Patients with a RODY

NO response or without RODY designation will be contacted by a different letter (attached recruitment letter for RODY NO patients). If the colonoscopy was performed at MGH, after an adenoma is resected from a patient at MGH, all gastroenterologists routinely contact their patients by mail with the results of their pathology. The recruitment letter will be included with the pathology results when possible, or it will be sent separately after the pathology report. If the colonoscopy and polypectomy were performed at another hospital, the MGH gastroenterologist will confirm the prior diagnosis of an adenoma through review of pathology reports. Their treating MGH gastroenterologist, regardless of whether the physician is study personnel, will sign the letter. If no response is received to this recruitment letter within two weeks (10 business days) a follow-up phone call or email will be placed by a research assistant/study coordinator (phone script/sample email attached). In some cases, the treating gastroenterologist may approach the patient following the colonoscopy that identified a polyp if he/she feels the patient would be a good candidate for the study. In these cases, the patients may not receive a recruitment letter as the primary method of contact. Instead, they will be directly contacted by phone or email (see call script/sample email) from a member of the research team prior to mailing the letter (if requested). Potential participants will have additional opportunities to ask any questions by contacting an investigator or a trained research coordinator. If the participant is interested in participating, eligibility will be assessed by the study coordinator (see script) and confirmed by the investigator through an additional check of the patients' medical record (see "Investigator Representation for Review of Protected Health Information Preparatory to Research" form). If eligibility is confirmed, the patient will be scheduled for their initial study visit and registered with OnCore by the study staff. The informed consent form will be mailed to the patient prior to the initial visit so that he or she can read it in detail, if requested by the participant. Eligible participants will provide written informed consent at the baseline visit prior to participation in the study. The consenting process will be performed by one of the trial's clinical investigators.

3.1 Eligibility Criteria

Participants must meet the following criteria on screening examination to be eligible to participate in the study:

- 3.1.1 Underwent screening or surveillance colonoscopy with removal of at least one adenoma;
- 3.1.2 Age 18-80 years.

This study will only include adult participants because colorectal carcinogenesis in children is more likely to be related to a cancer predisposition syndrome with distinct biological mechanisms compared with sporadic colorectal cancer in adults. Patients over age 80 will not be enrolled since the benefits and risks of AMR101 over the age of 80 have not yet been well-characterized.

- 3.1.3 The effects of AMR101 on the developing human fetus are unknown. For this reason, women of child-bearing potential must agree to use adequate contraception (hormonal or barrier method of birth control; abstinence) prior to study entry and for the duration of study participation. Should a woman become pregnant or suspect she is pregnant while she is participating in this study, she should inform her treating physician immediately.
- 3.1.4 Subjects must be able and willing to follow study procedures and instructions.
- 3.1.5 Ability to understand and the willingness to sign a written informed consent document.

3.2 Exclusion Criteria

Participants who exhibit any of the following conditions at screening will not be eligible for admission into the study.

- 3.2.1 Currently using or have used any fish oil supplement at any dose more than once per week within the last month.
- 3.2.2 Regularly consuming more than three servings of fish per week.
- 3.2.3 History of allergic reactions attributed to fish or compounds of similar chemical or biologic composition to omega-3 fatty acid.
- 3.2.4 Diagnosis of inflammatory bowel disease, liver or kidney disease, bleeding diathesis
- 3.2.5 Any prior diagnosis of gastrointestinal cancer (including esophageal, small intestine, colon, pancreatic), or any diagnosis of other cancers (with the exception of non-melanoma skin) in which there has been any active treatment within the last three years.
- 3.2.6 Known diagnosis of Familial Adenomatous Polyposis (FAP) or Hereditary Non-Polyposis Colorectal Cancer (HNPCC, Lynch Syndrome).
- 3.2.7 Any adenoma that was not completely removed during previous colonoscopy.
- 3.2.8 Known bleeding tendency/condition (e.g. von Willebrand disease) or history of peptic ulcer or gastrointestinal bleed requiring hospitalization, endoscopic complications, or contraindication to colonoscopy.
- 3.2.9 Current use of anticoagulant therapies, including Heparin, Warfarin, Dalteparin sodium, Bivalirudin, Argatroban, Lepirudin, Heparin Sodium, Heparin/Dextrose, and an unwillingness or inability to discontinue anticoagulants.
- 3.2.10 Uncontrolled intercurrent illness including, but not limited to, ongoing or active infection, symptomatic congestive heart failure, unstable angina pectoris, cardiac arrhythmia, or psychiatric illness/social situations that would limit compliance with study requirements.

- 3.2.11 Inability or unwillingness to abstain from non-protocol use of fish oil supplements or to provide blood, urine or stool samples or colon biopsies during the study.
- 3.2.12 Participants who are receiving any other investigational agents.
- 3.2.13 Inability or unwillingness to swallow pills.
- 3.2.14 Pregnant or breastfeeding.

The effects of AMR101 on the developing human fetus are unknown. For this reason, women of child-bearing potential must agree to use adequate contraception (hormonal or barrier method of birth control; abstinence) prior to study entry and for the duration of study participation. Should a woman become pregnant or suspect she is pregnant while she is participating in this study, she should inform her treating physician immediately. Similarly, lactating women are excluded from this study because there is an unknown but potential risk of adverse events in nursing infants secondary to treatment of the mother with AMR101. Consequently, breastfeeding should be discontinued if the mother is enrolled on the study.

- 3.2.15 Known positive test for human immunodeficiency virus (HIV), hepatitis C virus, or acute or chronic hepatitis B infection.

Participants with these infections are ineligible because they are at increased risk of significant complications in the perioperative period, and because fresh tissue from patients with these infections cannot be harvested for research purposes, per institutional policy. Appropriate studies will be undertaken in participants receiving combination antiretroviral therapy when indicated.

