4. REGISTRATION PROCEDURES

4.1 General Guidelines for DF/HCC Institutions

Institutions will register eligible participants in the Clinical Trials Management System (CTMS) OnCore. Registrations must occur prior to the initiation of protocol therapy. Any participant not registered to the protocol before protocol therapy begins will be considered ineligible and registration will be denied.

An investigator will confirm eligibility criteria and a member of the study team will complete the protocol-specific eligibility checklist.

The study staff will register the participant in OnCore.

Following registration, participants may begin protocol-specific therapy and/or intervention. Issues that would cause treatment delays should be discussed with the Overall Principal Investigator (PI). If the subject does not receive protocol therapy following registration, the subject must be taken off-study in the CTMS (OnCore) with an appropriate date and reason entered.

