5.5 General Concomitant Medication and Supportive Care Guidelines

Throughout the study, treating investigators may prescribe concomitant medications or treatments deemed necessary to provide adequate supportive care. However, participants may *not* receive:

- Other investigational agents;
- Anticoagulant therapies, including Heparin, Warfarin, Dalteparin sodium, Bivalirudin, Argatroban, Lepirudin, Heparin Sodium, Heparin/Dextrose, and other anticoagulant therapies;
- Any supplements that contain EPA.

All prescribed and non-prescription concomitant medications that are ingested, applied, or injected on an ongoing basis from signing of the informed consent, as well as changes in such concomitant medications, and any new concomitant medication taken while the participant is on study, should be recorded in the medical record. Concomitant medications for medically significant adverse events, which are ongoing at the end of study treatment and considered related to study treatment, should be followed until the adverse event is resolved or considered stable.

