6. DOSING DELAYS/DOSE MODIFICATIONS

Dose reduction will be made as indicated in the following table(s). The descriptions and grading scales found in the revised NCI Common Terminology Criteria for Adverse Events (CTCAE) version 5.0 will be utilized for dose reduction. A copy of the CTCAE version 5.0 can be downloaded from the CTEP website

http://ctep.cancer.gov/protocolDevelopment/electronic_applications/ctc.htm.

When the study staff is informed of a GI-related adverse event, dose reduction may be considered, according to the following dose de-escalation schema.

Dose Level	AMR 101 Dose
Initial Dose	4 grams/day, for the full course of the intervention
Level -1	2 grams/day, for the rest of the intervention period

Criteria for treatment reduction and suggested guidelines for the management of GI toxicities related to AMR 101 are summarized below. These general guidelines may be modified at the discretion of the investigator based on best clinical judgment at that time, but the reason for these reductions must be documented in the medical record. Any GI toxicities related to AMR 101 should be managed according to standard medical practice. These dose reductions are guidance for clinicians for use of this standard therapy.

Participants who report GI-related adverse events including but not limited to the adverse events described in the tables below will be offered dose reduction as well as the option to withdraw from the study.

Nausea	Management/Next Dose for AMR 101
≤ Grade 1	Reduce to dose level -1
Grade 2	Reduce to dose level -1
Grade 3	Reduce to dose level -1
Grade 4	Reduce to dose level -1

Vomiting	Management/Next Dose for AMR 101
≤ Grade 1	Reduce to dose level -1
Grade 2	Reduce to dose level -1
Grade 3	Reduce to dose level -1

Vomiting	Management/Next Dose for AMR 101
Grade 4	Reduce to dose level -1

Diarrhea	Management/Next Dose for AMR 101
≤ Grade 1	Reduce to dose level -1
Grade 2	Reduce to dose level -1
Grade 3	Reduce to dose level -1
Grade 4	Reduce to dose level -1

Constipation	Management/Next Dose for AMR 101
≤ Grade 1	Reduce to dose level -1
Grade 2	Reduce to dose level -1
Grade 3	Reduce to dose level -1
Grade 4	Reduce to dose level -1

Stomach pain	Management/Next Dose for AMR 101
≤ Grade 1	Reduce to dose level -1
Grade 2	Reduce to dose level -1
Grade 3	Reduce to dose level -1
Grade 4	Reduce to dose level -1

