7.1 Expected Toxicities

AMR101 may produce a hypersensitivity reaction in individuals with known hypersensitivity to shellfish/fish. Because AMR101 contains ethyl esters of omega-3 fatty acid, patients taking other anticoagulants may be at risk to develop a prolonged bleeding time; the risk of active bleeding is unknown.

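### Exclusion 3.2.3 bars fish allergy but does not name shellfish, although section 7.1 names shellfish/fish hypersensitivity as a risk with AMR101

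*Combined protocol and SAP*

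**What the plan says.** The allergy exclusion is item 3.2.3 in section 3.2 (Exclusion Criteria): "History of allergic reactions attributed to fish or compounds of similar chemical or biologic composition to omega-3 fatty acid".

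Section 7.1 (Expected Toxicities) names two groups at risk from the drug. The first is defined by allergy: "AMR101 may produce a hypersensitivity reaction in individuals with known hypersensitivity to shellfish/fish". The second is defined by concomitant treatment: "patients taking other anticoagulants may be at risk to develop a prolonged bleeding time".

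The second group is handled in two places. Item 3.2.9 addresses "Current use of anticoagulant therapies, including Heparin, Warfarin, Dalteparin sodium" and further named agents, for people who will not or cannot stop them. Section 5.5 then prohibits during the study "Anticoagulant therapies, including Heparin, Warfarin, Dalteparin sodium, Bivalirudin, Argatroban, Lepirudin, Heparin Sodium, Heparin/Dextrose, and other anticoagulant therapies".

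On process, section 3 states that "eligibility will be assessed by the study coordinator (see script) and confirmed by the investigator" through a further look at the medical record. Section 4.1 has an investigator confirm the criteria and adds that "a member of the study team will complete the protocol-specific eligibility checklist".

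**The concern.** The risk statement and the exclusion that should act on it do not cover the same people. Section 7.1 puts shellfish beside fish; 3.2.3 names only fish and compounds resembling omega-3 fatty acid. Read literally, the exclusion list admits someone with a shellfish-only allergy, and the investigator confirming eligibility has no item that clearly bars that person.

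What is at stake is participant safety. Section 11 says that only laboratory endpoints are used, so there is little individual benefit to set against a risk the protocol itself names. Participants dose themselves for 8 to 12 weeks and adverse events are checked by weekly telephone call, so screening is the point at which this risk can be prevented. The statistical conclusions of the trial do not depend on it.

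**Working it through.** The plan gives no figure on this point, so there is none to reproduce. The check is a comparison of text, followed by a rough count under an assumed prevalence.

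**Step 1: does any other provision cover a shellfish-only allergy?**

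| Provision | What it covers | Covers shellfish-only allergy? |
|---|---|---|
| 3.1 Eligibility | Prior adenoma, age, contraception, ability to comply and consent | No |
| 3.2.3 | Allergy to fish or to compounds similar to omega-3 fatty acid | Not named |
| 3.2.10 | Uncontrolled intercurrent illness | No; a history of allergy is not an uncontrolled illness |
| Other items in 3.2 | Nothing on allergy; no general item on hypersensitivity to the drug; no general investigator discretion to exclude for safety | No |
| 5.2 Pre-Treatment Criteria | Marked not applicable | No |
| 5.5 Concomitant medication | Investigational agents, anticoagulants, EPA supplements | No |
| 6 Dose modification | "When the study staff is informed of a GI-related adverse event, dose reduction may be considered" | No; gastrointestinal events only |
| 5.6 and 5.8 Stopping rules | Includes unacceptable adverse events (5.6) | Only after a reaction |

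The only other place where shellfish occur is the food list of the dietary questionnaire in Appendix A, which is not an eligibility rule.

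**Step 2: is the gap consistent with how the protocol treats risk elsewhere?** It is not. Of the two groups in 7.1, anticoagulant users are addressed at entry and on study, while the allergy group is covered only in part. Section 3 also keeps out people over 80, and pregnant or breastfeeding women, because the risk to them is unknown or poorly characterised. In 7.1 the possible reaction is stated, and nothing explains why shellfish-allergic people may enrol.

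**Step 3: how many people could this involve?** Inputs: n = 80 (section 13.2) and p, the proportion of otherwise eligible adults with a shellfish-only allergy. The documents do not give p. I assume 1%, 2% and 3%, and that such people volunteer at the same rate as others and are not screened out by any other route.

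- Expected number among 80: 80p
- Chance of at least one: 1 − (1 − p)^80
- Chance of more than three: upper tail of the binomial (80, p)
- Otherwise eligible people needed to enrol 80 once shellfish is excluded: 80 / (1 − p)

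| Assumed p | 80p | (1 − p)^80 | At least one | More than three | 80 / (1 − p) |
|---|---|---|---|---|---|
| 1% | 0.8 | 0.45 | 55% | 1% | 80.8 |
| 2% | 1.6 | 0.20 | 80% | 8% | 81.6 |
| 3% | 2.4 | 0.09 | 91% | 22% | 82.5 |

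No reaction rate is given, so the expected number of reactions cannot be derived.

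**The case against.** The best reply is that a warning is not a contraindication. Section 7.1 says only that a reaction may occur, and a protocol can disclose a risk without excluding everyone it mentions. Sections 2.2 and 2.3 describe the product as a fish-oil fatty acid ester with no listed shellfish ingredient, so a fish-based exclusion fits the product as described. The documents contain no evidence that a shellfish-only allergy carries real risk here. That stands, and it is why no harm rate is claimed. It does not reconcile the two sections: if the sponsor thinks the risk negligible, 7.1 should say so.

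A second reply is that a screener could read fish broadly, or use the similar-compounds limb of 3.2.3. This is arguable, but 7.1 treats shellfish and fish as separate terms, and the similar-compounds limb concerns resemblance to omega-3 fatty acid. Two screeners could reasonably decide differently, which is itself a reason to amend the wording.

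A third is that other safeguards exist: the gastroenterologist's permission before contact, the record check, the screening script, the checklist, weekly calls and serious adverse event reporting. The calls and the reporting act only after dosing. None of the others is described as asking about allergy. The script and checklist were not in the text reviewed and may already ask about shellfish, so the practical effect is uncertain.

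Finally, the 1–3% prevalence has no anchor in the documents. That is correct; the range only shows the order of magnitude.

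**Conclusion.** The concern holds. As written, 3.2.3 does not cover a group that 7.1 names as possibly reacting to AMR101, and no other criterion closes the gap before the first dose. Confidence is high on the wording and lower on the practical consequence, because the screening forms could not be seen. With n = 80 and an assumed 1–3% prevalence, enrolment of at least one such person is more likely than not (55% to 91%), provided nothing outside the written criteria screens them out. The matter is minor in scale and concerns participant safety only, but it should be corrected because doing so is nearly free.

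**What to change.** Insert shellfish after fish in exclusion 3.2.3, leaving the rest of the item unchanged, and put the same term in the coordinator's screening script (section 3) and the eligibility checklist (section 4.1). If the sponsor has grounds to regard a shellfish-only allergy as safe with this product, the alternative is to state those grounds in 7.1. Without such grounds, widening the exclusion is the safer choice.

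The cost is a wording amendment and a slightly smaller recruitment pool. At an assumed 1–3% prevalence, the expected loss is 0.8 to 2.4 people per 80, and about 81 to 83 otherwise eligible people would be needed to enrol 80. The expected loss is an average: more than three of 80 would be lost with probability 1%, 8% or 22% at 1%, 2% or 3%. The sample size calculation and the primary analysis need no change.
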